## 7.0 Study Withdrawal/Discontinuation

Participants will contribute data to the study under conditions of waiver of consent/assent, as our intervention is an improvement upon best practices that poses minimal to low additional risk to participants compared to standard of care. **Treatment**

**decisions on whether to act on the provided information will be made by the treating physician and the patient.**

[figure not shown]
Patients who seek to have their data removed from the study can do so at any time by contacting the study team.

## **8.0 Statistical Considerations**

Statistical Analysis Plan: Our primary endpoint will be the percentage of patients who had their penicillin allergy label removed prior to discharge, comparing those who received intervention versus controls. We will also assess the number of patients who underwent oral challenge with amoxicillin in both arms. We will assess these outcomes using intention-to-treat analysis, using an adjusted logistic regression model.

Power and Sample Size Considerations: With no intervention, we assume 0.5% of patients have their penicillin allergy label intentionally removed or receive a test dose challenge during current practice in a six month period based upon preliminary data at Vanderbilt. We can power our study to detect a clinically meaningful difference of 20 additional penicillin-allergic patients per 100 having their penicillin allergy label removed using our intervention. Preliminary data suggest that around 100 patients per month are admitted and discharged from the 8N medical unit, and that 15-20% of all patients admitted at Vanderbilt have a penicillin allergy listed in their chart. Hence, approximately 15-20 penicillin allergic patients would be eligible for inclusion in the intervention group per month.

Assuming pessimistically that a minimum of 10% of patients randomized to intervention will have their physician engage with the tool, leading to an allergy label removed, and that 0.1% of patients in the control group will have a penicillin allergy label removed during current practice, 1:1 allocation of participants, an alpha of 0.05, power of 0.8 and a two-sided test of proportions, we will need a minimum of 35 patients per group (70 total) to detect a minimally clinically meaningful 20% increase in penicillin allergy label removals or amoxicillin challenges. Much smaller sample sizes will be needed to see effects if higher engagement and utilization is observed.

Our study will be intentionally overpowered for the primary outcome of penicillin allergy label removal, in order to try and capture the effect of this intervention upon secondary outcomes of 1) Frequency of risk stratification tool usage by physicians, 2) Any reported adverse events associated with oral challenge, 3) Communication about penicillin allergy label removal in the discharge summary. 4) longer term assessment of durability of label removal (at 3-18 months following label removal) 5) antibiotic utilization and use and tolerance of penicillins following label removal at 3- 18 months. In addition, we will add the amended baseline demographic of health literacy.

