#### Adverse Events

1) Exclusion criteria include patients who are currently medically unstable and unable to receive study procedures, or patients whose primary care is received outside of Vanderbilt University Medical Center. We know that by restricting inclusion to patients who receive the majority of their care at Vanderbilt that this will enable better long term monitoring of adverse events via the EHR.

2) All adverse events will be discussed with and evaluated by a physician investigator as soon as the subject or study personnel report them.

3) Adverse events including SAEs upon initial amoxicillin challenge or upon subsequent administration of penicillin class drugs in patients whose penicillin allergy label has been removed, or any unanticipated problems will be appropriately reported to the IRB, safety monitor, and NIAID. In addition to the IRB review of adverse events outlined above, the PIs will meet at least quarterly with staff to discuss any problems that arise that could compromise patient safety. Meetings will be held more frequently to quickly rectify problems if they arise. When necessary, the IRB will be consulted for further guidance. This is particularly true for reactions, which, in their most severe forms, threaten life or function. A serious AE (SAE) or serious adverse drug experience (SADE) is any untoward medical occurrence that:

- Results in death
- Is life-threatening. "Life-threatening" refers to an event in which the subject is at risk of death at the time of the event; it does not refer to an event which hypothetically might have caused death if it were more severe (ICH E6).
- Requires inpatient hospitalization or prolongation of existing hospitalization
- Results in persistent or significant disability/ incapacity (as per reporter's opinion)
- Is a congenital anomaly/birth defect

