### Key secondary endpoints

The secondary endpoints for this trial include the following:

1. Tolerance of an amoxicillin oral challenge, which will be documented using a smart phrase to indicate tolerance or intolerance. This outcome is a binary variable, either yes= tolerated, or no =not tolerated, with relevant symptoms to be determined by chart review.
2. Uptake of the risk stratification tool: This is determined by whether patients with a penicillin allergy label in their chart receive a risk assessment. This is a binary variable, either the patient did or did not receive a risk assessment of their penicillin allergy.
3. Amoxicillin adverse events: In patients who did not tolerate their amoxicillin oral challenge, we will assess the types of adverse events that were reported.
  - a. An immediate allergic amoxicillin challenge adverse event will be defined as an adverse event reported in association with the amoxicillin challenge that includes symptoms of anaphylaxis or rash, with onset within 6 hours of the challenge dose being given.
  - b. A non-immediate allergic amoxicillin challenge adverse event will be defined as an adverse event such as rash that is potentially consistent with allergy, occurring within 24 hours of the dose being given.
  - c. A non-allergic amoxicillin challenge adverse event will be defined as an adverse event, such as gastrointestinal upset, reported in association with amoxicillin challenge, within 6 hours of the challenge dose being given.
4. Communication about penicillin allergy label removal in the discharge summary: This is determined by the presence of language about the penicillin allergy evaluation, challenge, and removal, in those patients who underwent penicillin allergy challenge. The outcome is a binary variable, as this information is either present, or absent.
  - a. This data will be obtained by manual chart review.
  - b. A smart phrase has previously been created that was encouraged to be used for this purpose, and its utilization will be extracted.
5. Longer term penicillin allergy label removal, over 3 months and 18 months of follow up. Among those who underwent a penicillin allergy label removal, whether the allergy remains out of the chart or is “ever/never” re-entered into the chart. The outcome is a binary variable at either 3 months or at 18 months.

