6. Time to penicillin allergy return: for those participants who underwent an allergy label removal, we will compare the time to return of the allergy label based on the date the label first re-appeared in the chart.
7. Antibiotic utilization: This is based on the presence of qualifying penicillin or cephalosporin treatment doses, during the same hospitalization, and at 3 months and 18 months of follow up.
  - a. Same hospitalization: Utilization of these antibiotics will be defined as “yes” or “no” during the initial hospitalization in which amoxicillin challenge could have occurred, as a binary variable.
  - b. Subsequent utilization: Utilization of these antibiotics will be defined as “ever/never” by 3 months and ever/never by 18 months of follow up, as a binary variable.
  - c. Drugs included in the definition of penicillins are predefined as:
    - i. Ampicillin
    - ii. Ampicillin/sulbactam (unasyn)
    - iii. Amoxicillin
    - iv. Amoxicillin/Clavulanate (augmentin)
    - v. Cloxacillin
    - vi. Dicloxacillin

- vii. Nafcillin
- viii. Penicillin G
- ix. Penicillin VK
- x. Piperacillin
- xi. Piperacillin/Tazobactam
- xii. Ticarcillin
- xiii. Ticarcillin/Clavulanate (timentin)

d. Drugs included in the definition of cephalosporins are predefined as:

- i. Cefadroxil
- ii. Cefprozil
- iii. Cefaclor
- iv. Cephalexin
- v. Cephalothin
- vi. Cefazolin
- vii. Cefoxitin
- viii. Cefotetan
- ix. Cefamandole
- x. Cefuroxime
- xi. Cefepime
- xii. Ceftriaxone
- xiii. Cefpodoxime
- xiv. Ceftazidime
- xv. Cefdinir
- xvi. Cefixime
- xvii. Ceftaroline
- xviii. Ceftobiprole
- xix. Ceftozolane-Tazobactam

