### **Safety endpoints**

The key safety endpoints for this trial are potentially associated adverse events with the amoxicillin challenge, these are prespecified as:

- Anaphylaxis
- Other potentially allergic symptoms during/after amoxicillin challenge- e.g. rash
- Nausea/Vomiting/GI symptoms only
- Other symptoms during amoxicillin challenge

For reactions to penicillin given during the hospital stay, the same events will be captured:

- Anaphylaxis
- Other potentially allergic symptoms during/after penicillin administration- e.g. rash
- Nausea/Vomiting/GI symptoms only
- Other symptoms during penicillin administration

Due to the nature and clinical course of patients receiving routine hospital care, a substantial number of adverse events are expected among participants, including but not limited to:

- Death
- Sepsis
- Renal failure

- Respiratory failure
- Heart failure
- Pneumonia or other / new infection
- DVT or PE
- Complications related to ICU procedures
- Arrhythmia
- Delirium
- Bowel ischemia
- Ileus
- Leukopenia or leukocytosis
- Anemia or thrombocytopenia
- Coagulopathy (DIC)
- Hypoglycemia
- Electrolyte abnormalities

These adverse events are common in hospitalized patients and are thus not expected to reflect safety of the treatment regimen. There is no plan to summarize or report these events.

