## Main Analysis

Prior to modeling the data, we will describe the presentation of the amoxicillin challenge, the response, any adverse events, the rate of penicillin allergy removal, and subsequent use of penicillin as follows:

- Patient response to amoxicillin challenge -as n (proportion of total PALs)
  - Pass/Fail
    - as n (proportion) of total challenges done

- Proportion of failed challenges in which hypotension was present
    - as n (proportion) of challenges failed
      - Hypotension defined as systolic blood pressure decrease of 30% compared to pre-challenge blood pressure.
- Patient allergy removed from the chart's allergy box- absent at discharge
  - as n (proportion of total PALs)
- Same hospitalization use of a penicillin antibiotic,
  - as n (proportion of total PALs)
- Adverse events associated with amoxicillin challenge,
  - as n (proportion) of total challenges
- Adverse events associated with same hospitalization use of a penicillin antibiotic
  - as n (proportion of total PALs),
- Allergy evaluation information present/absent in discharge summary,
  - as n (proportion of completed PALs assessed as low-risk)
- Number of subsequent VUMC healthcare encounters after the initial hospitalization
  - Outpatient
    - average n per patient
  - ED/observation
    - average n per patient
  - Hospitalization/Inpatient
    - average n per patient
  - Surgical
    - average n per patient
- Ratio of penicillin treatments per total patient healthcare encounters since study entry

**Primary model:** Penicillin allergy label removal will be compared between the two groups using an adjusted logistic regression mixed effects model. In addition to study group assignment, the model will be adjusted for the following baseline covariates: time from start of study, age, race/ethnicity, sex, comorbidity index, health literacy, and intervention unit as a random effect. We will additionally include intervention unit general acuity level, defined based on the average APRDRG for patients discharged from the unit during the study period. The magnitude of effect will be reported as odds ratios with confidence intervals. A critical two-sided p-value of 0.05 will be used to draw conclusions on the main effect of intervention.

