#### Reporting of Safety Events:

- Adverse events associated with amoxicillin challenge
  - as n (proportion) of total challenges
- Adverse events associated with same hospitalization use of a penicillin antibiotic
  - as n (proportion of total PALs)

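### Penicillin tolerance at 3-18 months after label removal, a protocol secondary outcome, has no SAP variable; in-hospital penicillin reactions have two unreconciled denominators, neither limited to patients given penicillin

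*Protocol*

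**What the plan says.** **After discharge.** The fifth secondary outcome in Protocol 8.0 covers antibiotic utilization and "use and tolerance of penicillins following label removal at 3- 18 months". Protocol 6.0 (Adverse Events) also requires reporting to the IRB, safety monitor and funder of adverse events "upon subsequent administration of penicillin class drugs in patients whose penicillin allergy label has been removed".

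The nearest SAP items, in section 3, are:

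- Endpoint 7, antibiotic utilization, is based on "qualifying penicillin or cephalosporin treatment doses, during the same hospitalization, and at 3 months and 18 months of follow up". After discharge it is an ever/never variable by 3 and by 18 months.
- Endpoint 1 is "Tolerance of an amoxicillin oral challenge, which will be documented using a smart phrase to indicate tolerance or intolerance".
- Endpoints 5 and 6 follow whether and when the label returns to the chart.
- Safety endpoints: "For reactions to penicillin given during the hospital stay, the same events will be captured".

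**In hospital.** SAP 10 (Main Analysis and Reporting of Safety Events) gives challenge reactions per challenge performed. The line "Adverse events associated with same hospitalization use of a penicillin antibiotic" is instead to be given "as n (proportion of total PALs". Main Analysis also lists "Same hospitalization use of a penicillin antibiotic" per total PALs. SAP 9 (Safety analysis set) says the between-group comparison of penicillin safety events will use the intent-to-treat set, which SAP 9 defines as everyone on a study unit for at least 24 hours. SAP 10 (Safety Analysis) plans group differences in event rates with 95% confidence intervals and does not restate a denominator.

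**The concern.** Protocol 2.0 aims to establish the safety and impact of single-dose challenge as a way of removing the label. Whether de-labelled patients tolerate penicillins when they later receive them bears directly on that aim. The protocol names it as an outcome, but the SAP defines no variable, denominator or interval for it.

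The in-hospital figure raises a separate problem of interpretation. A reaction rate per labelled patient is the product of how often penicillin is given and how often recipients react. Protocol 1.0 holds that the label causes avoidance of penicillins, so use may differ between groups. A difference in rates could then be read as a difference in tolerance when part or all of it reflects use. Leaving the base unstated adds to the ambiguity.

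**Working it through.** The documents state no figure on this point. The first two steps compare text; the others are illustrations, with assumptions marked.

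**1. Is there an SAP variable for later tolerance?**

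| SAP item | Penicillin given at 3-18 months? | Reaction recorded at 3-18 months? |
|---|---|---|
| Endpoint 1 | No (challenge only) | No |
| Endpoints 5-6 | No (label return) | No |
| Endpoint 7 | Yes | No |
| Safety endpoints, therapeutic penicillin | No (hospital stay) | No |
| Main Analysis, ratio of penicillin treatments to encounters | Yes | No |

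The Safety Analysis sentence on penicillin treatments has no time window, but the endpoint definition and the reporting list both confine these events to the stay. Label return is at best a partial proxy: it shows neither that a penicillin was given nor that a reaction occurred.

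**2. Are the two in-hospital bases the same?** As worded, SAP 2 and SAP 9 do not require a label. SAP 8 puts labelled patients at 10-15% of admissions, so read literally the bases differ by a factor of 1/0.15 = 6.7 to 1/0.10 = 10. Protocol 4.0 enrols labelled patients only, so PALs may be what is meant.

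**3. How many patients would inform later tolerance?**

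- Intervention unit-months, from 12 units and one-month steps (SAP 8), with the last unit live for 30 days (SAP 10): 12 + 11 + ... + 1 = 78.
- Intervention PALs at 10-15 per unit-month (SAP 8): 780-1170.
- De-labelled at 10% (the SAP's pessimistic minimum): 78-117. At 20% (its target difference, used here as a removal rate): 156-234.
- Exact two-sided 95% upper limit for 0 reactions in n patients: 1 - 0.025^(1/n).

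| Later penicillin use (assumed) | 10% removal: n (upper limit) | 20% removal: n (upper limit) |
|---|---|---|
| 10% | 8-12 (36.9-26.5%) | 16-23 (20.6-14.8%) |
| 20% | 16-23 (20.6-14.8%) | 31-47 (11.2-7.5%) |
| 40% | 31-47 (11.2-7.5%) | 62-94 (5.8-3.8%) |

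Control unit-months are 144 - 78 = 66, or 78 if one run-in month comes first (an assumed length). That gives 660-1170 control PALs, of whom 0.5% is about 3-6 de-labelled patients, too few for a group comparison.

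**4. How far could use alone move the per-PAL rate?** Per-PAL rate = use × risk per recipient. Assume 5% use in controls, 5% in intervention patients who keep their label, use u within the stay among the de-labelled, removal r, and a 2% risk per recipient in both groups. Intervention use = r × u + (1 - r) × 0.05.

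| r | u | Intervention use | Ratio to 5% | Per-PAL difference (points) |
|---|---|---|---|---|
| 10% | 10% | 5.5% | 1.1 | 0.01 |
| 10% | 20% | 6.5% | 1.3 | 0.03 |
| 10% | 40% | 8.5% | 1.7 | 0.07 |
| 20% | 10% | 6.0% | 1.2 | 0.02 |
| 20% | 20% | 8.0% | 1.6 | 0.06 |
| 20% | 40% | 12.0% | 2.4 | 0.14 |

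For example, 0.20 × 0.40 + 0.80 × 0.05 = 0.12, and (0.12 - 0.05) × 0.02 = 0.0014. The true difference per recipient is zero in every row.

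**The case against.** The case against has four parts.

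- **A base is named.** SAP 9 assigns the comparison to the intent-to-treat set, and SAP 10 reports the same events per total PALs. This stands: a reader might infer from the Safety Analysis paragraph that no denominator exists at all, and the SAP does not support that. The fault is two bases left unreconciled.
- **Per-PAL is legitimate and a per-recipient figure is not randomized.** Both are true. The per-PAL rate measures burden, and restricting to recipients conditions on something that happens after randomization. SAP 10 does not set out to compare safety inferentially. Main Analysis also prints use beside reactions, so a crude in-hospital ratio can be derived. That ratio is nevertheless unplanned and has no interval, and nothing comparable can be derived at 3-18 months.
- **Later reactions are reported anyway.** Protocol 6.0 does require this, so it would be wrong to infer that such reactions would go unnoticed. Case reporting without a count of patients exposed is still not the outcome in Protocol 8.0.
- **The yield is small.** With 16-47 exposed patients and an assumed 1-2% risk, fewer than one reaction is expected (47 × 0.02 = 0.94). The result could exclude only high reaction rates. This argues for a descriptive estimate with an interval, and does not justify dropping a stated outcome without saying so.

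**Conclusion.** The point holds in two parts. First, a secondary outcome in the protocol has no counterpart in the SAP. This rests on the text alone and is the more important part. Second, in-hospital therapeutic penicillin reactions are tied to two different bases. The rate differences do not say which applies, and neither isolates patients who received a penicillin.

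The second effect is modest on plausible inputs: a use ratio of 1.1-2.4 and a per-PAL difference of about 0.01-0.14 points from use alone. Every use and risk value there is an assumption, including equal use in controls and in intervention patients who keep their label.

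A reader might infer a much larger distortion, for instance a fourfold difference from 5% v 20% use. Under the same assumption about patients who keep their label, that would require same-stay use among the de-labelled of (20 - 4)/0.20 = 80% at 20% removal and (20 - 4.5)/0.10 = 155% at 10% removal, which is impossible. Nor should one expect the per-PAL comparison to reverse the per-recipient one: with risks of 2% in control and 1% in intervention, a reversal needs a use ratio above 2, which occurs in one of the six rows above.

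The primary analysis and the safety reporting of the challenge are unaffected. The change should be made, but the trial's main conclusion does not depend on it.

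**What to change.** 1. **SAP 3 (endpoint 7 and Safety endpoints).** Add a descriptive outcome: among de-labelled patients given a penicillin on the SAP's list by 3 and by 18 months, the number and proportion with a recorded reaction in the SAP's four categories, with an exact 95% confidence interval and no group comparison.
2. **SAP 10 (Main Analysis and Reporting of Safety Events).** Keep the per-PAL figure. Beside it, report reactions per patient given at least one therapeutic penicillin dose in that hospitalization, excluding the challenge dose, by group, with an exact 95% interval. Label it descriptive because it conditions on post-randomization use.
3. **SAP 10 (Safety Analysis).** State total PALs as the one denominator for the rate differences, and reconcile this with the intent-to-treat wording in SAP 9.

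The cost is SAP wording, one extra table row, and chart review of de-labelled patients who later receive a penicillin: about 16-47 at 10-20% removal and an assumed 20% use, or 8-94 across 10-40% use. This fits within the planned 18-month follow-up. The downsides are wide intervals, reactions treated outside the centre that may be missed, and new figures that are not randomized comparisons.

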## 9.0 Privacy/Confidentiality Issues

All data collected from patient medical records or through the risk stratification tool will be kept in a REDCap database which can only be accessed by key study personnel who have been given access and have a login and password. Identifiable information will not be linked or shared to data collected. All identifiable information will be stored in a study binder in a locked cabinet or within RedCAP. Only the PI and KSP on the study will have access to this information. Upon discontinuation of the study, the database will be purged of identifiers and kept within the HIPAA compliant RedCAP system. Therefore, we perceive the risks to privacy to be minimal.

We have developed our penicillin allergy risk stratification tool into a secure online questionnaire with data collecting ability within the RedCAP system, such that it can now serve as both an interactive educational tool for physicians and also collect data. This

tool and others to be developed will be utilized by KSP during retrospective chart review, as a means for collecting relevant data related to risk stratification and validating the instruments.

The only identifier collected by the current RedCAP risk stratification tool itself is the medical record number, to allow linkage with other data that will be collected in a separate, secure RedCAP database. A copy of the RedCAP risk stratification questionnaire is attached separately in file PenicillinAllergyRiskStratific.pdf.

The anticipated benefits to patients are much larger. Access to the information will allow us to determine the effectiveness of our proposed intervention compared to current practice in a pragmatic, patient-oriented, real world setting. Removal of unnecessary penicillin allergy labels, in turn, has impacts on major patient impacts as described on previous pages of this application.

Health literacy data are collected and entered into the EHR routinely by nurses as adult patients are admitted to Vanderbilt University Hospital. The Effective Health Communication Core maintains an IRB-approved data repository (#150406, PI: [name]) of the health literacy screening data (HEALS Database) collected during routine clinical care. The PI will provide the HEALS coordinator, added as KSP to this study, with a list of MRNs of the participants enrolled in this study via a HIPPA-compliant secure file transfer. The HEALS coordinator will then provide the PI with health literacy data for only the patients enrolled in this study, via a HIPPA-compliant secure file transfer. The health literacy data will be stored in a REDCap database which can only be accessed by key study personnel who have been given access and have a login and password.

